7.4. Replacement of Patients

Patients prematurely discontinued from study drug will not be replaced.

8. STUDY TREATMENTS

8.1. Investigational and Reference Treatments

Evinacumab or placebo will be supplied for IV administration. The 2 study treatment groups are:

- Evinacumab 20 mg/kg administered IV over a 1-hour infusion Q4W (± 4 days)
- Matching placebo administered IV Q4W (± 4 days)

Instructions on management of infusion reactions are provided in Section [8.4](#).

Instructions on dose preparation are provided in the pharmacy manual.

8.2. Background Treatment(s)

Prior to screening, all patients should be on a stable, lipid-lowering therapeutic regimen, which may include a statin, fibrate, niacin, or fish oils. Participants will be expected to continue their therapeutic regimen throughout the DBTP. There is no mandatory background therapy required for participation.

8.3. Dose Modification and Study Treatment Discontinuation Rules

8.3.1. Dose Modification

Dose modification for an individual patient is not allowed.

8.3.2. Study Drug Discontinuation

Patients who permanently discontinue from study drug should be encouraged to remain in the study. Those who agree and do not withdraw from the study will be asked to return to the clinic for all remaining study visits and assessments per the visit schedule, especially the week 52 visit, including the off-drug follow-up visits ([Table 1](#) and [Table 2](#)).

Patients who permanently discontinue from study drug and who opt to withdraw from the study (ie, are unable or unwilling to attend the study visits as described above) will be asked to complete study assessments at an early termination (ET) visit, per Section [9.1.2](#). These patients will then enter the off-drug treatment follow-up period, and should be followed for at least 20 weeks from the last dose of study drug or up to recovery or stabilization of any AE to be followed-up as specified in this protocol, whichever comes last. The off-drug follow-up period will include 2 in-clinic visits with assessments as specified under visit 16 and visit 17 ([Table 2](#)).

8.3.2.1. Reasons for Permanent Discontinuation of Study Drug

Study drug dosing will be permanently stopped in the event of:

- Evidence of pregnancy
- Severe, acute infusion reactions related to study treatment including, but not limited to, anaphylaxis
- Specific types of liver dysfunction (eg, Hy's law is met ([Guidance for Industry Drug Induced Liver Injury: Premarketing Clinical Evaluation FDA 2009]))

Liver impairment as evidenced by 1 or more of the following criteria and no other reason can be found to explain the following lab abnormalities, such as viral hepatitis A, B, or C; pre-existing or acute liver disease; or another drug capable of causing the observed injury:

- ALT or AST $>8 \times$ ULN, or
- ALT or AST $>5 \times$ ULN for more than 2 weeks, or
- ALT or AST $>3 \times$ ULN and total bilirubin $>2 \times$ ULN (or international normalized ratio [INR] >1.5)
- ALT or AST $>3 \times$ ULN with the appearance of fatigue, nausea, vomiting, right upper quadrant pain or tenderness, fever, rash, and/or eosinophilia ($>5\%$)
- Patient withdraws consent

8.3.2.2. Reasons for Temporary Discontinuation of Study Drug

The investigator may temporarily discontinue study drug dosing at any time, even without consultation with the medical monitor if the urgency of the situation requires immediate action and if this is determined to be in the patient's best interest. However, the Regeneron medical monitor should be contacted as soon as possible. Resumption of study drug dosing requires consultation and agreement between the investigator and the Regeneron medical monitor.

If a patient requires a prohibited medication at any time during the study, the principal investigator should contact the Regeneron medical monitor (except for illness requiring prompt treatment). Based on the discussions, study drug may be continued or temporarily or permanently discontinued.

8.4. Management of Acute Reactions

8.4.1. Acute Intravenous Infusion Reactions

Emergency equipment and medication for the treatment of infusion reactions must be available for immediate use. All infusion reactions must be reported as AEs (as defined in Section 10.2.4) and graded using the grading scales as instructed in Section 10.2.5.

8.4.1.1. Interruption of the Intravenous Infusion

The infusion should be interrupted if any of the following AEs are observed:

- Sustained/severe cough
- Rigors/chills
- Rash, pruritus (itching)
- Urticaria (hives, welts, wheals)
- Diaphoresis (sweating)
- Hypotension
- Dyspnea (shortness of breath)

- Vomiting
- Flushing

The reaction(s) should be treated symptomatically, and the infusion may be restarted at 50% of the original rate.

If investigators feel there is a medical need for treatment or discontinuation of the infusion other than described above, they should use clinical judgment to provide the appropriate response according to typical clinical practice.

8.4.1.2. Termination of the Intravenous Infusion

The infusion should be terminated and NOT restarted if any of the following AEs occur:

- Anaphylaxis*
- Laryngeal/pharyngeal edema
- Severe bronchospasm
- Chest pain
- Seizure
- Severe hypotension
- Other neurological symptoms (confusion, loss of consciousness, paresthesia, paralysis, etc)
- Any other symptom or sign that, in the opinion of the investigator, warrants termination of the IV infusion

*Consider anaphylaxis if the following is observed ([Sampson, 2006](#)): acute onset of an illness (minutes to several hours) with involvement of the skin, mucosal tissue, or both (eg, generalized hives, pruritus, or flushing, swollen lips-tongue-uvula) AND AT LEAST ONE OF THE FOLLOWING

- Respiratory compromise (eg, dyspnea, wheeze-bronchospasm, stridor, reduced peak expiratory flow, hypoxemia)
- Reduced blood pressure or associated symptoms of end-organ dysfunction (eg, hypotonia [collapse], syncope, incontinence)

8.5. Method of Treatment Assignment

Approximately 120 patients will be randomized in a 1:1 ratio to receive either evinacumab or placebo according to a central randomization scheme provided by an interactive voice response system (IVRS)/interactive web response system (IWRS) to the designated study pharmacist (or qualified designee).

8.6. Blinding

Study patients, the principal investigators, and study site personnel will remain blinded to all randomization assignments throughout the study. The Regeneron medical/study director, study

monitor, and any other Regeneron and contract research organization (CRO) personnel who are in regular contact with the study site will remain blinded to all patient randomization assignments.

Lipid results from blood samples collected after the randomization visit will not be communicated to the sites, and the sponsor's operational team will not have access to these laboratory results until after the final database is locked for this study.

One interim analysis is planned. The team performing the interim analysis will be external to Regeneron with the intent to reduce data bias in the patients ongoing at the time of the interim. No study personnel involved in the day-to-day conduct of the study will have access to any unblinded data before the final database is locked for this study.

8.7. Emergency Unblinding

Unblinding of treatment assignment for a patient may be necessary due to a medical emergency or any other significant medical event (eg, pregnancy) and when a treatment decision is contingent on knowing the patient's treatment assignment. Study drug will be discontinued for patients whose treatment has been unblinded (Section [8.3.2](#)).

- If unblinding is required:
 - Only the investigator will make the decision to unblind the treatment assignment.
 - Only the affected patients will be unblinded.
 - The designated study pharmacist(s)/designee at the study site will provide the treatment assignment to the investigator. If there is no study pharmacist, the investigator for the site will unblind/unmask the patient. Unblinding is performed using the IVRS/IWRS which will notify Regeneron.
 - The investigator will notify Regeneron and/or designee as soon as possible after unblinding the patient.

Treatment assignment is not to be provided to site personnel other than the unblinded study pharmacist (when applicable), at any time during the conduct of the study, except in the case of a true emergency and when a treatment decision is contingent on knowing the patient's treatment assignment. In the event that there is no study pharmacist, the individual at the site fulfilling that role will be the only unblinded member of the site personnel.

8.8. Treatment Logistics and Accountability

8.8.1. Packaging, Labeling, and Storage

A medication numbering system will be used to label blinded investigational study drug. Lists linking medication numbers with product lot numbers will be maintained by the groups (or companies) responsible for study drug packaging. In order to maintain the blind, these lists will not be accessible to individuals involved in study conduct.

Study drug will be stored at the site at a temperature of 2°C to 8°C; storage instructions will be provided in the pharmacy manual.

8.8.2. Supply and Disposition of Treatments

Study drug will be shipped at a temperature of 2°C to 8°C to the investigator or designee at regular intervals or as needed during the study. At specified time points during the study (eg, interim site monitoring visits), at the site close-out visit, and following drug reconciliation and documentation by the site monitor, all opened and unopened study drug will be destroyed/returned to the sponsor or designee.

8.8.3. Treatment Accountability

All drug accountability records must be kept current.

The investigator must be able to account for all opened and unopened study drug. These records should contain the dates, quantity, and study medication

- Dispensed to each patient
- Returned from each patient (if applicable), and
- Disposed of at the site or returned to the sponsor or designee.

All accountability records must be made available for inspection by the sponsor and regulatory agency inspectors; photocopies must be provided to the sponsor at the conclusion of the study.

8.8.4. Treatment Compliance

All doses of study drug will be administered in the clinic. All drug compliance records must be kept current and made available for inspection by the sponsor and regulatory agency inspectors.

8.9. Concomitant Medications

Any treatment administered from the time of informed consent to the final study visit will be considered concomitant medication. This includes medications that were started before the study and are ongoing during the study. Vaccination for COVID-19 should also be considered a concomitant medication.

8.9.1. Prohibited Medications

The following concomitant medications and procedures are prohibited during the study:

- Glybera®
- Lipid apheresis or plasma exchange
- Lomitapide
- Mipomersen and other antisense lipid therapies
- Systemic corticosteroids, with the following exceptions:
 - Used as replacement therapy for pituitary/adrenal disease with a stable regimen for at least 6 weeks prior to the screening visit
 - Used for ≤ 5 days during the treatment period for an acute illness as medically indicated

- Live or attenuated vaccination with replicating potential

8.9.2. Permitted Medications

The use of medications and nutritional supplements known to lower TG, including statins, fibrates, niacin, and omega-3s are permitted as long as therapy has been stable for at least 8 weeks prior to the screening visit. Patients must continue taking their background medical TG-modifying therapy for the duration of the study starting at screening and through the end of treatment visit.

Patients on thyroid replacement therapy can be included if the dosage of thyroxine has been stable for at least 12 weeks prior to the screening visit.

Topical, intra-articular, nasal, inhaled, and ophthalmic steroid therapies are not considered as 'systemic' and are allowed.

9. STUDY SCHEDULE OF EVENTS AND PROCEDURES

9.1. Schedule of Events

In light of the public health emergency related to COVID-19, the continuity of clinical study conduct and oversight may require implementation of temporary or alternative mechanisms. Examples of such mechanisms may include, but are not limited to, any of the following: phone contact, virtual visits, telemedicine visits, online meetings, non-invasive remote monitoring devices, use of local clinic or laboratory locations, and home visits by skilled staff. Additionally, no waivers to deviate from protocol enrollment criteria due to COVID-19 will be granted. All temporary mechanisms utilized, and deviations from planned study procedures in response to COVID-19, are to be documented as being related to COVID-19 and will remain in effect only for the duration of the public health emergency.

Study assessments and procedures for the DBTP are presented by visit in [Table 1](#), and in [Table 2](#) for the off-drug follow-up period.

Table 1: Schedule of Events for the DBTP

	Screening Period	Double-Blind Treatment Period (DBTP)												
		V1	V2	V3	V4	V5	V6	V7	V8	V9	V10	V11	V12	V13
Visit # (V)														
Week		0	4	8	12	16	20	24	28	32	36	40	44	48
Day	-28	1	29	57	85	113	141	169	197	225	253	281	309	337
Window (day)			±4	±4	±4	±4	±4	±4	±4	±4	±4	±4	±4	±4
Study Procedure														
Screening/Baseline:														
Inclusion/Exclusion	X	X												
Informed Consent	X													
Medical History ¹	X													
Height, Weight, BMI ²	X													
Demographics	X													
Amylase and Lipase		X												
FT4, TSH	X													
FSH (for women only) ³	X													
Randomization		X												
Treatment:														
Administer Study Drug ⁴		X	X	X	X	X	X	X	X	X	X	X	X	X
Concomitant Meds and Treatment	X	X	X	X	X	X	X	X	X	X	X	X	X	X
Efficacy:														
Lipid Profile ^{5,6}	X	X	X	X	X	X	X	X	X	X	X	X	X	X
Special Lipids ⁶		X						X						
Presence of Abdominal Pain (1-Item Question)	X	X	X	X	X	X	X	X	X	X	X	X	X	X
HAP-Pain Questionnaire	X	X	X	X	X	X	X	X	X	X	X	X	X	X
Safety:														
Weight		X	X	X	X	X	X	X	X	X	X	X	X	X
Vital Signs ⁷	X	X	X	X	X	X	X	X	X	X	X	X	X	X
Physical Examination	X	X												

	Screening Period	Double-Blind Treatment Period (DBTP)												
		V1	V2	V3	V4	V5	V6	V7	V8	V9	V10	V11	V12	V13
Visit # (V)														
Week		0	4	8	12	16	20	24	28	32	36	40	44	48
Day	-28	1	29	57	85	113	141	169	197	225	253	281	309	337
Window (day)			±4	±4	±4	±4	±4	±4	±4	±4	±4	±4	±4	±4
Study Procedure														
Electrocardiogram ⁸	X	X												
Adverse Events	X	X	X	X	X	X	X	X	X	X	X	X	X	X
Laboratory: ⁵														
Hematology	X	X												
Blood Chemistry	X	X	X	X		X		X		X		X		X
Pregnancy Test ^{9,10}	X	X	X	X	X	X	X	X	X	X	X	X	X	X
Pharmacokinetics and Immunogenicity Sampling:														
Drug Conc. Sample ¹¹		X	X	X	X	X	X	X	X	X	X	X	X	X
ADA and NAb sample ¹²		X				X				X				
Biomarkers:														
Biomarker		X							X					
Serum/Plasma ¹³														
Lipoprotein Analysis by NMR		X												
Optional Pharmacogenomics:														
DNA Sample (Optional) ¹⁴		X												
Other:														
Mandatory DNA Sample for FCS	X													
Genotyping for Subset of Patients ¹⁵														
Dietary Review	X	X	X	X	X	X	X	X	X	X	X	X	X	X
Alcohol Intake Review	X	X	X	X	X	X	X	X	X	X	X	X	X	X

Table 2: Schedule of Events for the Off-Drug Follow-up Period

	End of DBTP	Off Drug Follow-Up		
		V15	V16	End of Study V17
Visit # (V)	V15	V16		End of Study V17
Week	52	62		72
Day	365	435		505
Window (day)	±4	±7		±7
Efficacy:				
Lipid Profile ¹	X	X	X	
Special Lipids ¹	X		X	
Presence of Abdominal Pain (1-Item Question)	X	X	X	
HAP-Pain Questionnaire	X	X	X	
Safety:				
Concomitant Meds and Treatment	X	X	X	
Weight	X	X	X	
Vital Signs	X	X	X	
Physical Examination			X	
Electrocardiogram ²			X	
Adverse Events	X	X	X	
Laboratory : ³				
Hematology	X		X	
Blood Chemistry	X	X	X	
Pregnancy Test ^{4,5}	X		X	
Pharmacokinetics and Immunogenicity Sampling: ⁶				
Drug Conc. Sample	X		X	
ADA and NAb Sample	X		X	
Biomarkers:				
Biomarker Serum/Plasma	X		X	
Lipoprotein Analysis by NMR	X			
Other:				
Dietary Review	X	X	X	
Alcohol Intake Review	X	X	X	

9.1.1. Footnotes for the Schedule of Events Tables**9.1.1.1. Footnotes for Table 1 Schedule of Events (DBTP)**

1. Medical history should include detailed cardiovascular and pancreatitis history.
2. Height will be measured in meters (m). Body weight will be assessed using calibrated scales. Patients should void (empty bladder) prior to weight assessment. Patients should be wearing undergarments only and no shoes during weight assessments. Body weight will be recorded to the nearest 0.1 kg. Body mass index (BMI) is calculated as weight (kg)/height(m)².
3. Postmenopausal status will be confirmed by measurement of FSH.
4. At dosing visits, all assessments (including urine or serum pregnancy tests for WOCBP) should be performed before the dose of study drug is administered.
5. All blood samples should be collected before the administration of study drug. All samples should be collected following at least an 8-hour fast. Medications are permitted to be taken with water as medically indicated.
6. Lipids and lipoproteins (Lipid Profile): TC, TG, HDL-C, LDL-C will be measured. Special lipids: ApoC3, ApoB48, ApoB100, ApoB Total.
7. On dosing days, vital signs should also be measured, and AEs monitored pre-dose, at the end of study drug infusion, and at 30 minutes and 60 minutes post-end of infusion. Patients will be closely monitored for a minimum of 60 minutes after IV administration of study drug.
8. Electrocardiograms should be performed before blood is drawn.
9. Pregnancy test for WOCBP: A serum test will be done at the screening visit and a urine test will be done at all other visits indicated. Any positive urine test should be confirmed with a serum pregnancy test.
10. All patients will be reminded of protocol-specified contraception use and pregnancy reporting.
11. Blood samples for drug concentration and total ANGPTL3 should be obtained prior to AND at the end of infusion of study drug (within 30 minutes from the end of infusion).
12. Blood samples for ADA and NAb samples should be collected prior to the administration of study drug.
13. Residual biomarker samples as well as unused drug concentration and immunogenicity samples from the study may be utilized for future biomedical research (FBR) as permitted by patient consent and local regulatory policies. Samples may be stored for up to 15 years or as permitted by local regulatory policies, whichever is shorter, for FBR.
14. Patients who agree to participate in the genomics sub-study will be required to consent to this optional sub-study before collection of the samples. Whole blood samples for DNA extraction should be collected on day 1/baseline (pre-dose), but can be collected at a later study visit.

15. Mandatory DNA sample for FCS genotyping is only for patients who have no documentation of prior genotype testing that confirms the absence of FCS due to LoF mutations in *LPL*.

9.1.1.2. Footnotes for Table 2 Schedule of Events (Off Drug Follow-up Period)

1. Lipids and lipoproteins (Lipid Profile): TC, TG, HDL-C, LDL-C will be measured. Special lipids: ApoC3, ApoB48, ApoB100, ApoB Total.
2. Electrocardiograms should be performed before blood is drawn.
3. All samples should be collected following at least an 8-hour fast. Medications are permitted to be taken with water as medically indicated.
4. Pregnancy test for WOCBP: A urine test will be done at all other visits indicated. Any positive urine test should be confirmed with a serum pregnancy test.
5. All patients will be reminded of protocol-specified contraception use and pregnancy reporting.
6. Drug concentration should occur prior to and at the end of infusion of study drug, if applicable. Immunogenicity collection should occur prior to infusion of study drug, if applicable.

9.1.2. Early Termination Visit

Patients who are withdrawn from the study before the end of the DBTP (visit 16, week 52) will be asked to return to the clinic for an ET visit consisting of the end of DBTP assessments described under visit 16 (Table 2). After the ET visit, patients will enter the off-drug treatment follow-up period.

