Revised the definition of the study population	Broadened the inclusion criteria for the trial. In addition to enrolling patients with TG value >880 mg/dL at the screening visit, also allowing patients with a TG value at screening >500 mg/dL if they have a prior fasting measurement >1000 mg/dL or if they have had 2 or more episodes of pancreatitis in the past 24 months.	Clinical Study Synopsis, Target Population, Statistical Plan Section 3.2.1 Rationale for Study Design Section 2.1 Primary Objective Section 6.1 Study Description and Duration Figure 1 Study Flow Diagram Section 7.2.1 Inclusion Criteria, #3
Broadened the entry criteria with regard to fasting TG values at study entry and consequently removed Visit 2 during the Screening Period; Extended the time period for patients having a documented history of HTG from 15 to 24 months of screening	See rationale above. Since requiring only a single TG screening value, eliminating visit 2 which had the purpose of checking a second screening value. This decreases the burden on participants and sites, while still enrolling patients who have demonstrated high fasting TG values.	Clinical Study Protocol Synopsis, Objectives, Study Design, Study Duration Section 2.1 Primary Objective Section 3.1 Hypotheses Section 3.2.1 Rationale for Study Design Section 6.1 Study Description and Duration Section 7.2.1 Inclusion Criteria, Criterion #2 Table 1 Schedule of Events for DBTP Section 11.4.3.1 Primary Efficacy Analysis
Broadened the entry criteria with regard to BMI at study entry	Feedback from investigators and experts in this area have stated that a BMI range of 18-40 is too restrictive. Therefore the upper limit was increased to 45.	Section 7.2.1 Inclusion Criteria, Criterion #5
Added exclusion criterion for patients with a history of hypersensitivity to study drug or excipients, and for patients having received COVID-19 vaccination within 1 week of start of study medication.	The exclusion for hypersensitivity was an omission in the last version of the protocol that is now being updated. The exclusion for COVID-19 was added as the study drug has not been tested together with vaccines for COVID-19.	Section 7.2.2 Exclusion Criteria, new criteria #20, and #21 Section 8.9.1 Prohibited Medications

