Reduced the off-drug follow-up period from 48 weeks to 20 weeks and the total study duration from 100 weeks to 72 weeks	Feedback from investigators, experts, and potential patients has been that a 48-week off-drug follow-up period is excessive and discourages participation. Other studies have demonstrated that evinacumab serum concentrations are minimal (ie, <1 ug/mL and <1% of C _{max}) by 24 weeks after the last drug administration	Clinical Study Protocol Synopsis, Study Design, Study Duration Section 3.2.1 Rationale for Study Design Section 6.1 Study Description and Duration Figure 1 Study Flow Diagram Section 8.3.2 Study Drug Discontinuation Table 1 Schedule of Events for the DBTP Table 2 Schedule of Events for the Off-Drug Follow-up Period
Revised definition of study follow-up period	Patient disposition summaries were adjusted to align with the 20-week follow-up period. Simplified the definition of screened patients. Simplified the descriptions of TEAE summaries that will be provided.	Section 11.4.1 Patient Disposition Section 11.4.5.1 Adverse Events
Distinguished separate timepoints for collection of lipids and special lipids	This was an oversight in the last version of the protocol. Special Lipids (ApoC3, ApoB48, ApoB100, and ApoB Total) collections were reduced as was the original intention.	Table 1 Schedule of Events for the DBTP Table 2 Schedule of Events for the Off-Drug Follow-up Period Section 9.1.1.1 Footnotes for Table 1 Schedule of Events (DBTP), #6 Section 9.1.1.2 Footnotes for Table 2 Schedule of Events (Off Drug Follow-up Period), #1 Section 9.2.2.2 Fasting Blood Samples for Assessment of Lipid Profile (For Efficacy and PD Variables)
Specified that immunogenicity sample collection should occur prior to infusion	This corrects an error in the prior version. Immunogenicity only needs to be sampled prior to infusion.	Section 9.1.1.2 Footnotes for Table 2 Schedule of Events (Off Drug Follow-up Period), #6
Removed eligibility criteria redundant text	To minimize repetition of identical text to avoid discrepancies and enhance readability	Clinical Study Protocol Synopsis, Study Design
Added APOE genotypes to the list of genes encoding proteins in the LPL pathway	APOE genotypes will be explored when patients are sequenced to assess their response to evinacumab	Section 1 Introduction

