The screening period may last up to 28 days and consists of 1 visit. During the screening period, all patients will undergo the informed consent process and standard screening procedures. Laboratory assessments used to determine eligibility may be repeated once during the screening period. The fasting TG measurement can be repeated once for values >500 mg/dL but <880 mg/dL.

A mandatory sample for DNA isolation will be obtained for patients who do not have documentation of prior genetic testing in order to confirm the absence of FCS due to homozygous or compound heterozygous LoF mutations in *LPL*. For these patients, the results of the screening FCS genotyping confirming no homozygous or compound heterozygous LoF mutations in *LPL* must be available before the patient can be enrolled in the study.

Patients who have screen-failed are not eligible for rescreening, unless rescreening is discussed and agreed with the medical monitor.

After confirmation of eligibility, patients will proceed to visit 2 for randomization.

Double-Blind Treatment Period (Day 1 to Day 365)

Principal investigators, study site personnel, study patients, and the Regeneron study team will all be blinded to treatment during the DBTP.

Randomized patients will receive either evinacumab administered IV at a dose of 20 mg/kg IV or matching placebo Q4W (± 4 days) during the DBTP. On dosing days, all assessments and lab samples (including urine or serum pregnancy tests for WOCBP) should be performed before the dose of study drug is administered. All samples should be collected following at least an 8-hour fast. Medications are permitted to be taken with water as medically indicated. Electrocardiograms should be performed before blood is drawn. Additionally, vital signs should be measured, and AEs monitored pre-dose, at the end of study drug infusion, and at 30 minutes and 60 minutes post-end of infusion. Patients will be closely monitored for a minimum of 60 minutes after IV administration of evinacumab or matching placebo.

Efficacy and safety procedures, including a standard lipid panel, dietary and alcohol use review, and the completion of a pain questionnaire will be performed as outlined in the Schedule of Events ([Table 1](#)).

Serum samples for the determination of total evinacumab and total ANGPTL3 should be collected prior to AND at the end of infusion of study drug (within 30 minutes from the end of infusion).

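### A patient who withdraws may leave follow-up 20 weeks after the last dose, while the TEAE, contraception and pregnancy-reporting windows run 24 weeks; the early termination visit is also misnumbered (minor)

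*Protocol*

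**What the plan says.** **Twenty weeks from the last dose.** Protocol 8.3.2 covers a patient who stops study drug and also leaves the study. After an ET visit the patient enters off-drug follow-up and "should be followed for at least 20 weeks from the last dose of study drug", or until any adverse event under protocol follow-up has recovered or stabilised, whichever is later. That period contains "2 in-clinic visits with assessments as specified under visit 16 and visit 17". Protocol 6.1 also counts 20 weeks from the last dose, once for general monitoring and once for pregnancy status.

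**Twenty-four weeks from the last dose.** This is the length of the contraception requirement (7.2.2, criterion 19), of pregnancy reporting (10.1.3) and of the TEAE period (11.4.5.1, 168 days). Section 11.4.5.1 gives the expected duration of residual drug effect as its reason. SAP 4.8.1 keeps the 168 days.

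**Schedule.** In Table 1 the last dose is at Week 48, Day 337. The next schedule, "Table 2: Schedule of Events for the Off-Drug Follow-up Period", puts Week 52 at visit 15 (Day 365), Week 62 at visit 16 (Day 435) and Week 72 at visit 17 (Day 505).

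**Labels that do not match.** Protocol 9.1.2 calls the end of the double-blind period visit 16 and asks for an "ET visit consisting of the end of DBTP assessments described under visit 16 (Table 2". SAP 10.4.2 repeats the number and points to a Table 5; the SAP has Tables 1 to 3. The off-drug heading in Protocol 6.1 ends at Day 700.

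**The concern.** The shorter floor and the longer windows describe the same patient. A site that follows 8.3.2 to its stated minimum can close a patient out while the protocol still treats new events as treatment-emergent and still requires contraception. The amendment history points the same way: its reason for shortening follow-up is that drug concentrations are minimal "by 24 weeks after the last drug administration", which is 24 weeks and not 20. The SAP safety tables use the 168-day window, so events that nobody was scheduled to ask about would be missing from them.

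The visit number matters less. A site that went by the number 16 would use the Week 62 column at ET, which has fewer samples than the Week 52 column.

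**Working it through.** **1. The plan's own figure.** 168 days / 7 = 24.0 weeks, so the TEAE definition is consistent with itself.

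**2. Completers.** The last dose is on Day 337 and visit 17 on Day 505.
- 505 - 337 = 168 days = 24.0 weeks from the last dose.
- (505 - 365) / 7 = 20.0 weeks from the Week 52 visit.
- With windows of ±4 days on the dose and ±7 days on visit 17: from 498 - 341 = 157 days (22.4 weeks) to 512 - 333 = 179 days (25.6 weeks).
- Largest shortfall for an in-window completer: 168 - 157 = 11 days, or 11/168 = 6.5%.

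The schedule's 20 weeks therefore run from Week 52. Twenty weeks from the last dose would be Day 337 + 140 = Day 477. That is after visit 16 closes (Day 442) and before visit 17 opens (Day 498), so it matches no scheduled visit. For completers, the 20 weeks in 6.1 is a wording error.

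**3. Withdrawn patients.** Let d be the number of days from the last dose to the ET visit.
- At the bare minimum in 8.3.2: gap = 168 - 140 = 28 days = 16.7% of 168.
- If visit 17 is set 20 weeks after ET (day d + 140): gap = max(0, 28 - d).

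| d (days) | 0 | 7 | 14 | 21 | 28 or more |
|---|---|---|---|---|---|
| nominal gap (days) | 28 | 21 | 14 | 7 | 0 |

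The ±7-day window on visit 17 could add up to 7 days to these figures; the 140-day floor still caps the gap at 28.

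**4. Visit number.** Protocol 6.1 says that after screening "patients will proceed to visit 2 for randomization". With visits every four weeks, visit number = 2 + week/4, so Week 48 is visit 14 and Week 52 is 2 + 52/4 = visit 15. The Table 2 header is not cleanly legible in the public text, but this count and 8.3.2, which places visits 16 and 17 after ET, settle the matter without it.

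**5. What the wrong column would omit.** Seven assessments are marked at Week 52 and not at visit 16: special lipids, hematology, pregnancy test, drug concentration, ADA/NAb, biomarkers and NMR. Protocol 9.2.3.4 separately requires urine pregnancy testing at every scheduled visit after screening, which leaves six at risk. Five of the six are marked again at visit 17; NMR is not. SAP 1.2.4 drops the NMR and NAb analyses.

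**6. Likely origin (not part of the conflict).** The amendment history records "eliminating visit 2 which had the purpose of checking a second screening value"; one extra screening visit would have made Week 52 visit 16. It also records "Reduced the off-drug follow-up period from 48 weeks to 20 weeks and the total study duration from 100 weeks to 72 weeks"; 100 weeks x 7 = 700 days, the figure left in the 6.1 heading.

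**The case against.** The strongest reply is that the windows are different obligations. The TEAE period classifies events and the contraception rule binds the patient; neither creates a visit. Pregnancies stay reportable for 24 weeks whatever the date of the last visit (10.1.3). Serious events judged related stay reportable after the reporting period (10.1.1), and 8.3.2 extends follow-up for events already being followed. Patients who stop drug but stay in the study attend all remaining visits. Read together, 8.3.2, 9.1.2 and Table 2 most naturally put visit 17 at 20 weeks after ET. The patients concerned have already declined further visits.

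Most of this stands, and it limits the size of the point. It does not remove it: none of these rules provides a contact at which a new event that is non-serious, or serious but judged unrelated, would be found between 140 and 168 days. Nor does any of them carry scheduled pregnancy monitoring to the end of the contraception period.

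On the visit number, the objection largely succeeds. Section 9.1.2 also says Week 52 and end of the double-blind period, so a careful site would use the right column.

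A reader might infer that the slip costs a key secondary measurement. The documents do not support that. Fasting TG is in the lipid profile, which is marked at visit 16. Week 52 ApoC3 must fall in the SAP Week 52 window, which by the SAP 10.2 formula is Day 15 + 28 x 12 = 351 to Day 42 + 28 x 12 = 378; an ET sample taken before Day 351 is not the Week 52 value.

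**Conclusion.** The inconsistency is real and minor. For a patient who withdraws from the study, between 0 and 28 of 168 TEAE days (0% to 16.7%) may lack scheduled follow-up. The upper end needs either follow-up stopped at the bare 8.3.2 minimum or an ET visit on the day of dosing; under the natural reading the nominal gap closes once ET is 28 days after the last dose. The gap concerns new non-serious or unrelated events and scheduled pregnancy monitoring.

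Two stronger readings should be resisted. Four weeks of safety observation are not lost for everyone: an in-window completer is at most 11 days short, and nominally not short at all. Pregnancies after 20 weeks are not exempt from reporting.

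The visit, table and Day 700 errors are clerical. Nothing here touches the primary endpoint, power or alpha. The documents do not say how many patients withdrew, or whether any were still in follow-up after the August 2022 decision to stop the study (SAP 1). The SAP is descriptive throughout, but it still builds its safety tables on the 168-day window.

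**What to change.** **Main change.**
- Protocol 8.3.2: raise the minimum from 20 to 24 weeks from the last dose, met by visit 17 or, if visit 17 falls earlier, by one later contact.
- Protocol 6.1: state that patients and pregnancy status are monitored to 24 weeks from the last dose; for completers this is visit 17 within its window.
- Leave the 20-week cut-off for incomplete follow-up in 11.4.1 as it is. A compliant completer may reach visit 17 at 157 days, which passes the 140-day rule but would fail a 168-day one. The price is that a withdrawn patient last seen at 20 weeks would miss the new 8.3.2 floor without being counted as incomplete, which is acceptable for a disposition count.

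**Clerical corrections.**
- Protocol 9.1.2 and SAP 10.4.2: change visit 16 to visit 15 (twice in each).
- SAP 10.4.2: change Table 5 to Table 3.
- Protocol 6.1 off-drug heading: change Day 700 to Day 505.

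**Cost.** Wording in two documents and at most one extra contact per withdrawn patient. The completer schedule does not change.
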